1. SYNOPSIS

Title:	Phase II study of pembrolizumab plus ramucirumab in metastatic gastric or GEJ adenocarcinoma as salvage treatment
Design:	A single-arm, open-label, single-center Phase II study
Sponsor:	Samsung Medical Center Principal Investigator :[name] M.D, Ph.D.
Objective	
1) Primary Objective: To estimate preliminary overall response rate (ORR) of combination therapy of Ramucirumab and Pembrolizumab in patients with metastatic gastric or GEJ adenocarcinoma
 
2)Secondary Objectives: To assess secondary measures of clinical efficacy
 
 - Best Overall Response Rate: BORR - Disease Control Rate: DCR - Progression-Free Survival:PFS - Overall Survival: OS - Duration of Overall Response: DOR & maximal tumor shrinkage 
3) Biomarker Objectives: Integrative immune-genomic analysis to identify association of response with prevalent markers (e.g. PD-L1 expression, EMT signature, T-cell and cytolytic immune signatures, RNA-seq, hypermutation, pre and post cfDNA cancer panel genomics (Changes of TMB and landscape of genome), PFS/OS/safety
 
 ✓ Fresh tissues at baseline if clinically feasible/ in advanced to 3 cycles(if clinically feasible) ✓ (archival tissue only is not acceptable for study entry due to limited analysis on archival tissues) ✓ RNA sequencing to understand the mechanism of action of pembrolizumab and ramucirumab in responders and non-responders. ✓ Evaluating changes of component of Immune cells and cytokines in blood. ✓ Describe the association between EBV gastric cancer /or high PDL1 MSS and clinical activity in subjects who metastatic gastric or GEJ adenocarcinoma.
Subjects:	Patients with metastatic gastric or GEJ adenocarcinoma; EBV positive or PDL1 CPS≥5 .
Inclusion & Exclusion Criteria	
Inclusion Criteria
 
Each patient must meet the following criteria to be enrolled in this study:
 
 1. The patient is ≥18 years of age.

[Type here]

[Type here]

[Type here]

	
 2. The patient who has received an adequate information and provided informed consent for all the study-specific procedures in advance 3. The patient has histologically or cytologically confirmed gastric carcinoma, including gastric adenocarcinoma or GEJ adenocarcinoma. (Patients with adenocarcinoma of the distal esophagus are eligible if the primary tumor involves the GEJ.) patient has metastatic disease or locally recurrent, unresectable disease. 4. The patient's tumor tissue must have the pre-defined characteristics as follows; EBV+ or PDL1 CPS\geq5 5. The patient has measureable or evaluable disease as determined by standard computed tomography (CT) or magnetic resonance imaging (MRI) imaging. Examples of evaluable, nonmeasurable disease include gastric, peritoneal, or mesenteric thickening in areas of known disease, or peritoneal nodules that are too small to be considered measurable by Response Evaluation Criteria in Solid Tumors (RECIST version 1.1) 6. The patient has experienced disease progression during first-line treatment or second-line therapy for metastatic disease. 
 • Acceptable prior chemotherapy regimens for this protocol are combination chemotherapy regimens that include platinum and/or fluoropyrimidine components (acceptable prior platinum agents are cisplatin, carboplatin, or oxaliplatin; acceptable prior fluoropyrimidine agents are 5-FU, capecitabine, or S-1). Regimens including a third agent, such as an anthracycline or a taxane, are acceptable provided a fluoropyrimidine and/or a platinum were used. • Recurrence during or within 6 months of completion of adjuvant chemotherapy (capecitabine, 5-FU, or TS-1) will be considered as first-line chemotherapy. 7. No prior exposure to anti-PD1 antibody or ramucirumab 8. The patient has an Eastern Cooperative Oncology Group performance status (ECOG PS) score of 0 or 1. 9. Patients must have acceptable bone marrow, liver and renal function measured within 28 days prior to administration of study treatment as defined below: 
 ✓ Haemoglobin \geq9.0 g/dL ✓ Absolute neutrophil count (ANC) \geq 1.5 x 10⁹/L ✓ Platelet count \geq100 x 10⁹/L ✓ Total bilirubin \leq 1.5 x institutional upper limit of normal (ULN) ✓ AST (SGOT)/ALT (SGPT) \leq 3.0 x institutional upper limit of normal unless liver metastases are present in which case it must be \leq 5x ULN ✓ Serum creatinine \leq1.5 x institutional ULN ✓ Glomerular filtration rate < 45 mL/min in assessed by standard methods in the laboratory ✓ Urinary protein is \leq1+ on dipstick or routine urinalysis ✓ (INR) \leq1.5 and (PTT) \leq5 seconds above the ULN (unless receiving anticoagulation therapy). Patients on anticoagulation therapy with
--	--

[Type here]

[Type here]

[Type here]

	
unresected primary tumors or local tumor recurrence following resection are not eligible
 
10. Female patients of childbearing potential must have a negative pregnancy test (urine), must not be breastfeeding and using adequate contraceptive measures.
 
Female patients must use a highly effective contraceptive measure from screening until 4 months after the last dose of drug. All methods of contraception (except for total abstinence) should be used in combination with the use of a condom by a male sexual partner for intercourse (see Restrictions below). (or vasectomy)
 
Female patients must have evidence of non-childbearing potential by fulfilling one of the following criteria at screening:
 
a. Post-menopausal women defined as aged more than 50 years and amenorrhoeic for at least 12 months following cessation of all exogenous hormonal treatment.
 
b. Documentation of irreversible surgical sterilisation by hysterectomy, bilateral oophorectomy, or bilateral salpingectomy, but not tubal ligation.
 
11-1. For the duration of the study and for 1 week after the last study drug administration, sexually active male patients must be willing to use barrier contraception i.e. condoms with all sexual partners. Where the sexual partner is a 'women of child-bearing potential' who is not using effective contraception, men must use a condom (with spermicide) during the study and for 6 months after the last dose of a study drug. (or vasectomy)
 
12. Mandatory biopsy during the screening window prior to dosing and at progression (if clinically feasible)
 
Exclusion Criteria
 
Patients who meet any of the following criteria will be excluded from participation in this study:
 
 1. The patient has documented and/or symptomatic, encephalitis, brain or leptomeningeal metastases. 2. The patient has experienced any Grade 3 to 4 GI bleeding within 3 months prior to enrollment. 3. The patient has experienced myocardial infarction, transient ischemic attack, cerebrovascular accident, or unstable angina, within 6 months prior to enrollment. 4. The patient has a history of deep vein thrombosis (DVT), pulmonary embolism (PE), or any other significant thromboembolism (venous port or catheter thrombosis or superficial venous thrombosis are not considered "significant") during the 3 months prior to first dose of protocol therapy. 5. Has received a live vaccine within 30 days prior to the first dose of study drug. Examples of live vaccines include, but are not limited to, the following: measles, mumps, rubella, varicella/zoster (chicken pox), yellow fever, rabies, Bacillus Calmette–Guérin
--	---

[Type here]

[Type here]

[Type here]

	
(BCG), and typhoid vaccine. Seasonal influenza vaccines for injection are generally killed virus vaccines and are allowed; however, intranasal influenza vaccines (eg, FluMist®) are live attenuated vaccines and are not allowed.
 
 6. The patient has an ongoing or active infection, symptomatic congestive heart failure, unstable angina pectoris, symptomatic or poorly controlled cardiac arrhythmia, uncontrolled thrombotic or hemorrhagic disorder, or any other serious uncontrolled medical disorders in the opinion of the treating physician. 7. The patient has ongoing or active psychiatric illness or social situation that would limit compliance with treatment. 8. The patient has uncontrolled or poorly controlled hypertension (>160 mmHg systolic or 
 i. >100 mmHg diastolic for >4 weeks) despite standard medical management. 9. The patient has a serious or nonhealing wound, ulcer, or bone fracture within 28 days prior to enrollment. 10. The patient has received chemotherapy, radiotherapy, immunotherapy, or targeted therapy for gastric cancer within 2 weeks prior to enrollment. 11. The patient has received any investigational therapy within 30 days prior to enrollment. 12. The patient has undergone major surgery within 28 days prior to enrollment, or subcutaneous venous access device placement within 7 days prior to enrollment. 13. The patient has received prior therapy with an agent that directly inhibits VEGF (including bevacizumab), or VEGF Receptor 2 activity, or any antiangiogenic agent and immunotherapy. 14. The patient is receiving chronic antiplatelet therapy, including aspirin, nonsteroidal anti-inflammatory drugs (NSAIDs; including ibuprofen, naproxen, and others), dipyridamole or clopidogrel, or similar agents. Once-daily aspirin use (maximum dose 325 mg/day) is permitted. 15. The patient has a known allergy to any of the treatment components. 16. Has had a prior anti-cancer monoclonal antibody (mAb) within 4 weeks prior to study Day 1 or who has not recovered (i.e., ≤ Grade 1 or at baseline) from adverse events due to agents administered more than 4 weeks earlier. 17. Has active autoimmune disease that has required systemic treatment in the past 2 years (i.e. with use of disease modifying agents, corticosteroids or immunosuppressive drugs). Replacement therapy (eg., thyroxine, insulin, or physiologic corticosteroid replacement therapy for adrenal or pituitary insufficiency, etc.) is not considered a form of systemic treatment. 18. Has a history of (non-infectious) pneumonitis that required steroids or has current pneumonitis. 19. Has an active infection requiring systemic therapy. 20. Has a known history of Human Immunodeficiency Virus (HIV) (HIV 1/2 antibodies). 21. Has known active Hepatitis B or Hepatitis C (e.g., HCV RNA [qualitative]
--	--

[Type here]

[Type here]

[Type here]

Pembrolizumab + Ramucirumab (Ver 2.5, Oct 2024)

	
is detected). Chronic HBV infection with anti-viral agent prophylaxis is allowed.
 
22. Has known liver cirrhosis at a level of Child-Pugh B (or worse) or cirrhosis (any degree) and a history of hepatic encephalopathy or clinically meaningful ascites resulting from cirrhosis. Clinically meaningful ascites is defined as ascites from cirrhosis requiring diuretics or paracentesis.
 
23. The patient is pregnant or breastfeeding

Goal:	To estimate efficacy and safety of combination therapy of Ramucirumab and Pembrolizumab in patients with metastatic gastric or GEJ adenocarcinoma
Planned Sample Size:	
: A maximum of 26 patients (considering 5% drop out rate) will be recruited to this single-arm phase II trial.
 
In this single-arm phase II trial, 25 people were calculated using Simon's two-stage design and a total of 26 patients will be recruited to account for a 5% dropout rate. The sample size is calculated by use of a two-stage minimax Simon's design to control the type I error at 5 % for null hypothesis that, for arm, the true response was 15 % or below and to have 85 % of power if the true response was 40 % or higher. 15 evaluable patients are to be treated in the first stage. If 1 or fewer response are observed in the first stage, the arm will be stopped. If at least 2 responses are observed in the first stage, 10 additional evaluable patients are to be entered onto the second stage. At the final analysis, the null hypothesis will be rejected if at least 7 responses are observed in 25 evaluable patients. RR is reported with its exact 95% CI.

Duration of Study:	Until 100% enrollment from approval regulatory authority
Study design (Dosage & Treatment):	
Patients will continue to receive study treatment, until they demonstrate objective disease progression (determined by modified RECIST 1.1) or until they meet any other discontinuation criteria.
 
 - Ramucirumab 8mg/kg on q2W - Pembrolizumab 200mg on q3W (pembrolizumab first followed by ramucirumab when concurrently administered on the same day)

	

The diagram illustrates the study timeline. It begins with a 'Screening' phase, followed by 'Cycle 1 (42 days)'. A 'Baseline Fresh Tissue Biopsy' is performed at the start of Cycle 1. Treatment days are marked as D1, D8, D15, D22, D29, and D36. Ramucirumab (R) is administered on D1, D15, and D29. Pembrolizumab (P) is administered on D1 and D22. A legend specifies: R: Ramu : 8mg/kg on D1, D15, D29 (every two weeks); P: Pembro : 200mg on D1, D22 (every three weeks).

 

If ramucirumab had to be stopped due to intolerable toxicity, pembrolizumab will be continued until unacceptable toxicity, disease progression or upto 35 cycles.

Specimen for biomarker and Genetic analysis	
1. Tumor Biopsy Tumor biopsies will be obtained from all subjects in the study. However, tumor biopsy can be exempted in cases considered as not safe or not accessible. It may be performed twice as below if possible.
 
1) Pre-treatment : Obtained at screening (Day 28) from the primary site.2) If disease progresses, optional tumor biopsy may be obtained after it is confirmed. 
2. Blood Collection For analysis of biomarker(ct DNA), peripheral blood of 10 ml will be collected from all patients at every cycle D1 and at confirmed disease progression.

Method for Assessment:	
1. Efficacy assessment
 
Objective Response Rate (ORR) : The proportion of the patients who have achieved complete response (CR) or partial response (PR) with confirmation. (Tumor response will be evaluated according to RECIST Ver. 1.1)
 
CT or MRI scans of the chest, abdomen, and pelvis, the tumor burden assessment method used at baseline, should also be used for each subsequent follow-up assessment.
 
If a patient discontinues treatment prior to progression (and/or is receiving follow-up cancer treatment), the patients' follow up monitoring should be continued until objective disease progression as defined by RECIST 1.1.
 
Categorization of objective tumor response assessments will be based on the modified RECIST 1.1 response criteria: CR (complete response), PR (partial response), SD (stable lesion), and PD (disease progression).
 
The progression of the target lesion (TL) is calculated compared to when the tumor burden was at a minimal level (ie, the minimum sum of diameters previously recorded during the trial). If not advanced, tumor response (CR, PR, SD) is calculated compared to baseline tumor measurements obtained prior to initiation of treatment.

[Type here]

[Type here]

[Type here]

	
For patients with only non-measurable disease from at baseline, categorization of objective tumor response assessment will be based on the modified RECIST 1.1 response criteria: CR, PD, non-CR/non-PD.
 
If the investigator is not sure whether progression has occurred, especially if there is a reaction to a non-target lesion (NTL) or a new lesion develops, if clinically necessary, dosing can be continued before next scheduled visit and be advisable to re-evaluate the patient's condition.
 
If progress is confirmed in the repeat scan, the progress date should be declared as the first scan date.
 
Secondary efficacy assessment will be conducted as follows:
 
 Best Overall Response Rate (BORR) is defined as the proportion of the patients who have achieved CR or PR at least once. Disease Control Rate (DCR) is defined as the proportion of the patients with a documented CR, PR, and SD (results will be provided by confirmed and unconfirmed). Progression-Free Survival (PFS) is defined as the time from first administration of investigational drug to the earlier date of PD or death due to any cause. Overall Survival (OS) is defined as the time from first administration of investigational drug to death due to any cause. Duration of Overall Response (DOR) is defined as the time from the first date of assessment as CR or PR to the earlier date of PD or death due to any cause. Maximal Tumor Shrinkage(MTS) is defined as rate of change in tumor size relative to the baseline at the time of best improvement. 
2. Safety assessment
 
The severity of all AEs will be graded for laboratory toxicity and symptoms according to NCI-CTCAE Ver. 5.0. For the events that are not pre-defined in terms under NCI-CTCAE, Investigator should assign a numeric grade of “1” to “5” using the definitions as Mild, Moderate, Severe, Life-threatening, Death, respectively based on maximal intensity.
 
3. Biomarker assessment
 
To collect and store diagnostic and/or archival tumour samples and any fresh tumour biopsies (pre-treatment if clinically feasible and before 3 cycles if clinically feasible) for potential future exploratory research into factors that may influence development and/or response to ramucirumab in combination with pembrolizumab. Next generation sequencing from these samples and/or other protein based exploratory analysis will be carried out. Fresh tissues at baseline is required if clinically feasible

--	---

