6.1 Inclusion Criteria

Each patient must meet the following criteria to be enrolled in this study:

1. The patient is ≥ 18 years of age.
2. The patient who has received an adequate information and provided informed consent for all the study-specific procedures in advance
3. The patient has histologically or cytologically confirmed gastric carcinoma, including gastric adenocarcinoma or GEJ adenocarcinoma. (Patients with adenocarcinoma of the distal esophagus are eligible if the primary tumor involves the GEJ.) patient has metastatic disease or locally recurrent,

[Type here]

[Type here]

[Type here]

Pembrolizumab + Ramucirumab (Ver 2.5, Oct 2024)

unresectable disease.

4. The patient's tumor tissue must have the pre-defined characteristics as follows ;
EBV+ or PDL1 CPS \geq 5
5. The patient has measureable or evaluable disease as determined by standard computed tomography (CT) or magnetic resonance imaging (MRI) imaging. Examples of evaluable, nonmeasurable disease include gastric, peritoneal, or mesenteric thickening in areas of known disease, or peritoneal nodules that are too small to be considered measurable by Response Evaluation Criteria in Solid Tumors (RECIST version 1.1)
6. The patient has experienced disease progression during first-line treatment or second-line therapy for metastatic disease.
 - Acceptable prior chemotherapy regimens for this protocol are combination chemotherapy regimens that include platinum and/or fluoropyrimidine components (acceptable prior platinum agents are cisplatin, carboplatin, or oxaliplatin; acceptable prior fluoropyrimidine agents are 5-FU, capecitabine, or S-1). Regimens including a third agent, such as an anthracycline or a taxane, are acceptable provided a fluoropyrimidine and/or a platinum were used.
 - Recurrence during or within 6 months of completion of adjuvant chemotherapy (capecitabine, 5-FU, or TS-1) will be considered as first-line chemotherapy.
7. No prior exposure to anti-PD1 antibody or ramucirumab. Or ramucirumab can participate if the investigator determines that there is a clinical benefit.
8. The patient has an Eastern Cooperative Oncology Group performance status (ECOG PS) score of 0 or 1.
9. Patients must have acceptable bone marrow, liver and renal function measured within 28 days prior to administration of study treatment as defined below:
 - ✓ Haemoglobin \geq 9.0 g/dL
 - ✓ Absolute neutrophil count (ANC) $\geq 1.5 \times 10^9$ /L
 - ✓ Platelet count $\geq 100 \times 10^9$ /L

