10.1.1 Tumor Evaluation

Modified RECIST 1.1 criteria will be used to assess patient response to treatment by determining PFS and ORR. The modified RECIST 1.1 guidelines for measurable, non-measurable, target and non-target lesions and the objective tumour response criteria (complete response, partial response, stable disease or progression of disease).

The methods of assessment of tumour burden used at baseline, CT or MRI scans of chest, abdomen and pelvis must be used at each subsequent follow-up assessment.

Following the baseline assessment, efficacy for all patients will be assessed by objective tumour assessments every 6 weeks relative to date of first dose until objective disease progression as defined by modified RECIST 1.1. See Study Schedule (Table 1) for further details.

[Type here]

[Type here]

[Type here]

Pembrolizumab + Ramucirumab (Ver 2.5, Oct 2024)

If a patient discontinues treatment (and/or receives a subsequent cancer therapy) prior to progression then the patient should still continue to be followed until objective disease progression as defined by modified RECIST 1.1.

Categorisation of objective tumour response assessment will be based on the modified RECIST 1.1 criteria of response: CR (complete response), PR (partial response), SD (stable disease) and PD (progression of disease). Target lesion (TL) progression will be calculated in comparison to when the tumour burden was at a minimum (i.e. smallest sum of diameters previously recorded on study). In the absence of progression, tumour response (CR, PR, SD) will be calculated in comparison to the baseline tumour measurements obtained before starting treatment.

For patients with non-measurable disease only at baseline, categorisation of objective tumor response assessment will be based on the modified RECIST 1.1 criteria of response: CR, PD and Non CR/Non PD.

If the investigator is in doubt as to whether progression has occurred, particularly with response to NTL (non-target lesion) or the appearance of a new lesion, it is advisable to continue treatment until the next scheduled assessment or sooner if clinically indicated and reassess the patient's status. If repeat scans confirm progression, then the date of the initial scan should be declared as the date of progression.

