 - b. Treatment cycle defined herein as 6 weeks; however, there will be no treatment interruption or break between cycles. Patients will continue to undergo treatment according to program protocol until there is evidence of disease progression, toxicity requiring cessation, withdrawal of consent, or until other withdrawal criteria are met.
 - c. End of therapy evaluations will be performed at the discontinuation of therapy; patients should be followed for at least 30 days after last dose of protocol therapy to ensure sufficient safety monitoring and any AEs reported unless another therapy has been commenced and the AE is thought related to post-program therapy. Written informed consent must be obtained prior to any program-specific pretreatment evaluations and before patient enrollment.
 - d. WOCBP must have a negative serum pregnancy test within 7 days prior to enrollment.
 - e. To be obtained within 28 days prior to enrollment only for patients with prior anthracycline therapy. Subsequent evaluations are not required, but may be done at the discretion of the patient's physician if warranted by dyspnea or other relevant symptoms.
 - f. Baseline imaging to determine the extent of disease and identify metastases, and tumor assessments should be performed within 14 days prior to enrollment, and every 6 weeks (± 3 days) until documented progression for patients with disease status of complete response (CR), partial response (PR), or stable disease (SD), and/or for patients who have discontinued program therapy due to toxicity or reasons other than progressive disease.
 - g. Including temperature, pulse rate, respiration rate, and blood pressure; to be obtained before, during, and at the completion of each infusion.
 - h. In situations where hemoglobin is less than 9 g/dL (5.58 mmol/L) and there are signs or symptoms of bleeding, a hematology profile should be performed weekly until hemoglobin is ≥ 9 g/dL (5.58 mmol/L) and any bleeding-related signs or symptoms have resolved or been adequately investigated.
 - i. Every 6 weeks or in accordance with local regulations, whichever is of shorter duration.
 - j. All SAEs considered at least possibly related to ramucirumab and pembrolizumab will be followed until resolution, stabilization, return to baseline, or until deemed irreversible.

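### The disease control rate has no place for Non-CR/Non-PD, so eligible patients with controlled, non-measurable disease cannot count as controlled

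*Combined protocol and SAP*

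**What the plan says.** Four places in the combined protocol and SAP bear on this.

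- **Eligibility.** Inclusion criterion 5 (synopsis and Section 6.1) reads: "The patient has measureable or evaluable disease as determined by standard computed tomography (CT) or magnetic resonance imaging (MRI) imaging". It gives wall, peritoneal or mesenteric thickening and very small peritoneal nodules as examples of evaluable, non-measurable disease. A patient with no measurable lesion can therefore enter.
- **Response categories.** For patients with only non-measurable disease at baseline, the synopsis says that assessment "will be based on the modified RECIST 1.1 response criteria: CR, PD, non-CR/non-PD". Section 10.1.1 agrees: it "will be based on the modified RECIST 1.1 criteria of response: CR, PD and Non CR/Non PD". Neither list contains PR or SD.
- **DCR definition.** In the synopsis, under secondary efficacy: "Disease Control Rate (DCR) is defined as the proportion of the patients with a documented CR, PR, and SD". Results are to be given confirmed and unconfirmed. Non-CR/Non-PD is not mentioned.
- **Analysis section.** Section 13.1.1 defines ORR over all patients who received at least one dose. Section 13 does not mention DCR and gives it no denominator.

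**The concern.** The response categories and the endpoint definition do not fit together. Non-CR/Non-PD is the category for a patient with non-measurable disease who has neither progressed nor reached CR, and it is missing from the DCR numerator. Such a patient could go many months without progression and still not count as controlled.

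DCR is a named secondary endpoint in a trial of at most 26 patients, so a few patients handled this way would visibly change the reported rate. The change would come from the category label and not from the treatment. Two analysts with the same data could also report different rates, one following the definition literally and the other treating Non-CR/Non-PD as SD.

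**Working it through.** **Is there a planned figure to reproduce?** No. The documents state no planned DCR, threshold, test or power for DCR. The check is therefore of the definition, followed by a count of its effect.

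**Inputs**
- N = 26, the maximum recruitment (synopsis and Section 12); 25 evaluable patients in the two-stage design.
- DCR numerator: CR, PR and SD (synopsis).
- Categories for non-measurable disease only: CR, PD, Non-CR/Non-PD (synopsis, Section 10.1.1).
- Denominator: not given for DCR. Taken as all treated patients, as Section 13.1.1 does for ORR.
- k, the number with non-measurable disease only: not in the documents. Assumed to be 2 to 5, for illustration.
- c, the share of those k patients who are controlled: not in the documents. Assumed to be 57.4%, a value borrowed from the earlier pembrolizumab study in Section 4.4.1 only to have a plausible figure; 70% is used as a second value.

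**Formulas**
- DCR as written = (CR + PR + SD) / N
- DCR with the missing category = (CR + PR + SD + Non-CR/Non-PD) / N
- Shortfall = m / N, where m is the number with best response Non-CR/Non-PD

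The shortfall is zero if m = 0 and otherwise always lowers DCR.

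**Per patient:** 1/26 = 3.8 points (1/25 = 4.0 points).

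**Illustration.** Assume that none of the k patients reaches CR and that the control rate c is the same in both groups. The expected m is k × c, and the expected shortfall is k × c / 26.

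| k of 26 | Shortfall at c = 57.4% | DCR as written, if 57.4% are controlled | Shortfall at c = 70% |
|---|---|---|---|
| 0 | 0 | 57.4% | 0 |
| 2 | 2 × 0.574 / 26 = 4.4 points | 53.0% | 5.4 points |
| 4 | 4 × 0.574 / 26 = 8.8 points | 48.6% | 10.8 points |
| 5 | 5 × 0.574 / 26 = 11.0 points | 46.4% | 13.5 points |

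**Does any other text close the gap?** Section 10.1.1 and the synopsis calculate CR, PR and SD against baseline tumour measurements, then give non-measurable patients their own list. The documents thus keep SD and Non-CR/Non-PD apart. The criteria are called modified RECIST 1.1, but no modification that maps one category to the other is described. No text removes these patients from DCR.

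**The case against.** The best reply is that a working analyst would treat Non-CR/Non-PD as the counterpart of SD and no harm would follow. That may happen, but the plan does not say so, and it lists the two as separate categories.

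Three other objections stand and limit the point.
- The DCR denominator is not stated. That these patients count as failures rests on reading the definition's reference to patients as all those treated. If they were meant to be excluded, the plan would have to say so.
- The number of such patients is unknown and may be zero.
- DCR is secondary and descriptive, and the two-stage rule in Section 12 does not use it.

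A reader might also infer more than the documents support.
- **Missed scans.** Footnote f of Appendix 1 continues imaging "until documented progression for patients with disease status of complete response (CR), partial response (PR), or stable disease (SD") and does not name Non-CR/Non-PD. Sections 7.3 and 10.1.1 nevertheless require imaging every 6 weeks until progression, the latter expressly for all patients. The footnote is a wording mismatch only.
- **A distorted comparison with 57.4%.** The Section 4.4.1 figure is itself CR + PR + SD: 3 + 12 + 20 = 35, and the percentages reported there imply 61 patients, so 35/61 = 57.4%. Nothing says how that study classed non-measurable disease, and the plan makes no comparison of DCR with it.
- **A faulty shrinkage endpoint.** Maximal tumour shrinkage "is defined as rate of change in tumor size relative to the baseline at the time of best improvement". It is plainly missing for patients with nothing measured. That is not an error in the plan, and no rule imputes it.
- **A loss of 7.7 to 19.2 points.** This is 2/26 to 5/26 and requires every one of 2 to 5 such patients to be controlled, with none in CR. It is an upper bound for those numbers, not an expected size.

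**Conclusion.** The point holds as a flaw in the definition of one secondary endpoint. Followed literally over all treated patients, the DCR rule cannot credit control in non-measurable disease short of CR, and it understates DCR by exactly m/N, or 3.8 points per patient at N = 26. Under the stated assumptions (2 to 5 of 26 with non-measurable disease only, about 57% of them controlled, none in CR), the expected shortfall is about 4 to 11 points. It is zero if no such patient enrols. The direction follows from the definition and the denominator reading; the size depends on a number that the documents do not give. The primary ORR analysis and the two-stage decision are untouched by this DCR definition.

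**What to change.** Before analysis, amend the synopsis definition so that DCR is the proportion of all treated patients with best response CR, PR, SD or Non-CR/Non-PD, the last applying only to patients with non-measurable disease only at baseline. Put the same definition and denominator in Section 13.1, where DCR does not now appear.

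Restricting DCR to patients with measurable disease is also coherent, but it describes a narrower population than the one enrolled. It is best reported as an optional supplement, with the number of patients in each group.

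Adding Non-CR/Non-PD to Appendix 1 footnote f would align it with Section 10.1.1. This is tidying of wording.

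The cost is a few lines of text. No extra patients, data or scans are needed, because Section 10.1.1 already requires the assessments and the category for these patients.
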